## **12. PLANS FOR DISSEMINATING AND COMMUNICATING STUDY RESULTS**

In the event of any prohibition or restriction imposed (e.g., clinical hold) by an applicable competent authority in any area of the world, or if Optum becomes aware of any new information which might influence the evaluation of the benefits and risks of a Pfizer product, Pfizer should be informed immediately.

**16. ANNEX 1. LIST OF STANDALONE DOCUMENTS**

None.

090177e1a5be86fe\Approved\Approved On: 19-Mar-2026 15:57 (GMT)

## 17. ANNEX 2. CODE LISTS

*CPT copyright 2024 American Medical Association (AMA). All rights reserved.*

*Fee schedules, relative value units, conversion factors and/or related components are not assigned by the AMA, are not part of CPT, and the AMA is not recommending their use. The AMA does not directly or indirectly practice medicine or dispense medical services. The AMA assumes no liability for data contained or not contained herein.*

*CPT is a registered trademark of the American Medical Association.*

### 17.1. Appendix I – COMIRNATY 2023-2024 Formula

The following CPT and NDC codes are sourced from the Immunization Information Systems (IIS) at the Center for Disease Control and Prevention ([CDC, 2023b](#)). Other codes will be included as they become available.

#### 17.1.1. CPT Codes

91318	Severe acute respiratory syndrome coronavirus 2 (SARS-CoV-2) (coronavirus disease [COVID-19]) vaccine, mRNA-LNP, spike protein, 3 mcg/0.3 mL dosage, tris-sucrose formulation, for intramuscular use
91319	Severe acute respiratory syndrome coronavirus 2 (SARS-CoV-2) (coronavirus disease [COVID-19]) vaccine, mRNA-LNP, spike protein, 10 mcg/0.3 mL dosage, tris-sucrose formulation, for intramuscular use
91320	Severe acute respiratory syndrome coronavirus 2 (SARS-CoV-2) (coronavirus disease [COVID-19]) vaccine, mRNA-LNP, spike protein, 30 mcg/0.3 mL dosage, tris-sucrose formulation, for intramuscular use

#### 17.1.2. NDC Codes

00069-2362-01	Ages 12 years and older; VIAL, SINGLE-DOSE, 30 mcg/0.3 mL
00069-2392-01	Ages 12 years and older; SYRINGE, PRE-FILLED, 30 mcg/0.3 mL
59267-4331-01	Ages 5 through 11 years; VIAL, SINGLE-DOSE, 10 mcg/0.3 mL
59267-4315-01	Ages 6 months through 4 years; VIAL, MULTI-DOSE, 3 DOSES, 3mcg / 0.3 mL AFTER DILUTION

## 17.2. Appendix II – Comparator Codes

### 17.2.1. COVID-19 Vaccine 2023-2024 Formulations Other than the COMIRNATY 2023-2024 Formula

#### 17.2.1.1. Moderna Spikevax

##### 17.2.1.1.1. CPT Codes

91322 -- Severe acute respiratory syndrome coronavirus 2 (SARS-CoV-2) (coronavirus disease [COVID-19]) vaccine, mRNA-LNP, 50 mcg/0.5 mL dosage, for intramuscular use

91321 -- Severe acute respiratory syndrome coronavirus 2 (SARS-CoV-2) (coronavirus disease [COVID-19]) vaccine, mRNA-LNP, 25 mcg/0.25 mL dosage, for intramuscular use

##### 17.2.1.1.2. NDC Codes

80777-0102-04 -- Ages 12 years and older; VIAL, SINGLE-DOSE, 50 mcg/0.5 mL

80777-0102-01 -- Ages 12 years and older; SYRINGE, PRE-FILLED, 50 mcg/0.5 mL

80777-0287-07 -- v25 mL

#### 17.2.1.2. Novavax COVID-19 Vaccine, Adjuvanted

##### 17.2.1.2.1. CPT codes

91304 -- Severe acute respiratory syndrome coronavirus 2 (SARS-CoV-2) (coronavirus disease [COVID-19]) vaccine, recombinant spike protein nanoparticle, saponin-based adjuvant, preservative free, 5 mcg/0.5 mL dosage, for intramuscular use

0041A -- Immunization administration by intramuscular injection of severe acute respiratory syndrome coronavirus 2 (SARS-CoV-2) (coronavirus disease [COVID-19]) vaccine, recombinant spike protein nanoparticle, saponin-based adjuvant, preservative free, 5 mcg/0.5mL

0042A -- Immunization administration by intramuscular injection of severe acute respiratory syndrome coronavirus 2 (SARS-CoV-2) (coronavirus disease [COVID-19]) vaccine, recombinant spike protein nanoparticle, saponin-based adjuvant, preservative free, 5 mcg/0.5mL

---

 CPT copyright 2024 American Medical Association. All rights reserved.

0044A -- Immunization administration by intramuscular injection of severe acute respiratory syndrome coronavirus 2 (SARS-CoV-2) (coronavirus disease [COVID-19]) vaccine, recombinant spike protein nanoparticle, saponin-based adjuvant, preservative free, 5 mcg/0.5mL

**17.2.1.2.2. NDC Codes**

80631-0105-01 -- Ages 12 years and older; VIAL, MULTI-DOSE, 5 DOSES, 5 mcg/0.5 mL

**17.2.2. Other Vaccines**

CPT and NDC codes are sourced from the Immunization Information Systems (IIS) at the Center for Disease Control and Prevention ([CDC, 2023c](#)). Other codes will be included as they become available.

**17.2.2.1. CPT Codes**

90630, 90653-90664, 90666-90668, 90672-90674, 90682-90689, 90694, 90724, 90756	Influenza virus vaccine
90380-90381, 90678-90679, 96380-96381	Respiratory syncytial virus vaccine
90470	H1N1 immunization
90476-90477	Adenovirus vaccine
90581	Anthrax vaccine
90585, 90728	Tuberculosis BGC vaccine
90611, 90622	Smallpox/monkeypox vaccine
90619-90621, 90644, 90733-90734	Meningococcal vaccine
90625, 90725	Cholera vaccine
90626-90627, 90738	Tick-borne/Japanese encephalitis virus vaccine
90632-90636, 90730	Hepatitis A vaccine

 CPT copyright 2024 American Medical Association. All rights reserved.

90636, 90739-90740, 90743-90748, 90759, 90731 	Hepatitis B vaccine
90645-90648, 90737	Hemophilus influenza type B vaccine
90649-90651	Human Papillomavirus vaccine
90665	Lyme disease vaccine
90669-90671, 90732	Pneumococcal vaccine
90675-90676, 90726	Rabies vaccine
90680-90681	Rotavirus vaccine
90690-90693	Typhoid vaccine
90696-90702, 90714-90715, 90720-90723	Diphtheria vaccine
90696-90703, 90714-90715, 90723	Tetanus vaccine
90696-90698, 90700, 90715, 90723	Pertussis vaccine
90704, 90707, 90709-90710	Mumps vaccine
90705, 90707-90708, 90710	Measles vaccine
90706, 90707-90710	Rubella vaccine
90696-90698, 90712-90713	Poliovirus vaccine
90710, 90716	Varicella virus vaccine
90717	Yellow fever vaccine
90727	Plague vaccine
90736, 90750	Zoster (shingles) vaccine
90758	Ebolavirus vaccine
90584, 90587	Dengue vaccine

 CPT copyright 2024 American Medical Association. All rights reserved.

### 17.2.2.2. NDC Codes

The below list includes generic vaccine names classified by therapeutic use. Codes for generic vaccines are based on the Hierarchical Ingredient Code List (HICL) system proprietary to First Databank. All associated NDC codes will be utilized. Other vaccines will be included as they become available.

Adenovirus vaccine, live

Anthrax vaccine

Anthrax vaccine, adsorbed

BCG vaccine

BCG vaccine, live

Cholera vaccine

Dengue vaccine

Diphtheria, pertussis, tetanus, and haemophilus influenzae type B vaccine

Hepatitis A virus vaccine

Hepatitis A virus and hepatitis B virus vaccine

Hepatitis B and haemophilus influenzae type B vaccine

Hepatitis B, diphtheria, and poliomyelitis virus vaccine

Hepatitis B, haemophilus influenzae type B, and meningococcal vaccine

Hepatitis B virus vaccine

HPV vaccine

Influenza A (H1N1) vaccine

Influenza A (H1N1) vaccine, live

Influenza virus vaccine

Influenza virus vaccine, trivalent

Influenza virus vaccine, trivalent, live

Japanese encephalitis vaccine

Measles and rubella vaccine  
Measles, mumps, and rubella vaccine  
Measles vaccine, live, attenuated  
Mumps vaccine, live  
Plague vaccine  
Poliomyelitis vaccine, killed  
Poliomyelitis vaccine, live  
Rabies vaccine  
Rabies vaccine, human diploid  
Rotavirus vaccine, live  
Rubella and mumps vaccine  
Rubella vaccine  
Smallpox, monkeypox, live  
Smallpox vaccine, live  
Staphylococcus vaccine  
Typhoid vaccine  
Varicella virus vaccine, live  
Yellow fever vaccine  
Zoster vaccine, live

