**Variables:**

- *Exposures:* Exposure to the COMIRNATY 2023-2024 Formula will be defined by the presence of National Drug Codes (NDC) on pharmacy claims or Healthcare Common Procedure Coding System (HCPCS) codes on medical claims.
- *Outcomes:* The pre-specified safety outcomes of interest include the following: acute disseminated encephalomyelitis (ADEM), anaphylaxis, Bell's palsy, cerebral venous sinus thrombosis (CVST), convulsions/seizures (non-febrile), encephalomyelitis, glomerulonephritis, Guillain-Barré syndrome, herpes zoster, immune-mediated myositis, immune thrombocytopenia, Kawasaki disease, multi inflammatory syndrome (in children and adults), multiple sclerosis (MS), myocardial infarction (MI), myocarditis/pericarditis, pulmonary embolism (PE), hemorrhagic stroke, ischemic stroke, and transverse myelitis. Study outcomes will be identified through claims indicators using published validated claims-based algorithms with high performance when available.
- *Covariates:* Baseline covariates will include information related to patient demographics, comorbidities, COVID-19 vaccination, healthcare utilization, and medication history. Additional baseline covariates will be identified on an empiric basis by examining the most frequently occurring diagnoses, drugs dispensed, and procedures performed among individuals with and without COMIRNATY 2023-2024 Formula exposure. Demographic

090177e1a5be86fe\Approved\Approved On: 19-Mar-2026 15:57 (GMT)

attributes will be determined on the vaccination/cohort entry date, while other factors will be assessed in the one year prior to the vaccination date or cohort entry date.

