### **9.4.1. Optum Pre-Adjudicated Claims Database**

The database includes pre-adjudicated medical claims, supplemented with adjudicated pharmacy claims and health plan enrollment information. As claims for pharmacy services are typically submitted electronically by the pharmacy at the time prescriptions are filled or vaccinations are administered and are updated in the underlying database on a weekly basis, they are not included in the pre-adjudicated feed. The pre-adjudicated medical claims encompass hospital and physician claims that are submitted and processed daily from a large US commercial health plan. The individuals included in the pre-adjudicated medical claims database are fully insured by the health plan, which provides reimbursement of medical and pharmacy services regardless of site of care, and individuals are geographically diverse within the US. The claims adjudication process involves numerous assessments and adjustments and may result in claims being returned to the provider for revision or sent for payment processing. The pre-adjudicated claims are maintained in a database that allows for the capture of up to three years of prior data. These pre-adjudicated claims have been used for research previously, and for federally funded public health surveillance ([Dore et al., 2012](#); [FDA, 2021b](#); [Shoabi et al., 2023](#); [Wong et al., 2023](#); [Moll et al., 2023](#); [Schneider et al., 2023](#)).

The data include demographics, details from pharmacy claims (reflecting dispensings), and all pre-adjudicated medical and facility claims, including information on the types of services

---

 CPT copyright 2024 American Medical Association. All rights reserved.

*Fee schedules, relative value units, conversion factors and/or related components are not assigned by the AMA, are not part of CPT, and the AMA is not recommending their use. The AMA does not directly or indirectly practice medicine or dispense medical services. The AMA assumes no liability for data contained or not contained herein.*

*CPT is a registered trademark of the American Medical Association.*

or procedures and their accompanying diagnoses. The coding of medical claims conforms to insurance industry standards, including:

- Use of designated claims forms (e.g., physicians use the CMS-1500 format and hospitals use the UB-04 format)
- International Classification of Diseases, 10th Revision, Clinical Modification (ICD-10-CM) diagnosis codes and procedure codes

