$$\begin{aligned} & \text{logit}\{P(T_i = 1 \mid \mathbf{X}_i)\} \\ &= \beta_0 + \beta_1 \text{Sex (binary)}_i + \beta_2 \text{Age (categorical)}_i \\ &+ \beta_3 \text{Calendar month (categorical)}_i + \beta_4 \text{Geographic region (categorical)}_i \\ &+ \beta_5 \text{Asthma (binary)}_i + \beta_6 \text{Non-malignant blood disorders (binary)}_i \\ &+ \beta_7 \text{Chronic lung disease (binary)}_i + \beta_8 \text{Down syndrome (binary)}_i \\ &+ \beta_9 \text{Heart disease (binary)}_i \\ &+ \beta_{10} \text{History of SARS-CoV-2 infection (binary)}_i \\ &+ \beta_{11} \text{Immunocompromised status (binary)}_i \\ &+ \beta_{12} \text{Kidney disorders (binary)}_i + \beta_{13} \text{Liver disorders (binary)}_i \\ &+ \beta_{14} \text{Neurological or neurodevelopmental conditions (binary)}_i \\ &+ \beta_{15} \text{Malignant neoplasms (binary)}_i + \beta_{16} \text{Obesity (binary)}_i \\ &+ \beta_{17} \text{Type II diabetes (binary)}_i \\ &+ \beta_{18} \text{Number of hospitalizations in prior year (continuous)}_i \\ &+ \beta_{19} \text{Number of emergency room visits in prior year (continuous)}_i \\ &+ \beta_{20} \text{Number of outpatient encounters in prior year (continuous)}_i \\ &+ \beta_{21} \text{Seasonal influenza vaccination (binary)}_i \\ &+ \beta_{22} \text{RSV vaccination (binary)}_i + \beta_{23} \text{Systemic immunomodulators (binary)}_i \\ &+ \beta_{24} \text{Oral corticosteroids (binary)}_i + \beta_{25} \text{Antivirals (binary)}_i \\ &+ \beta_{26} \text{Antibiotics (binary)}_i + \beta_{27} \text{Identified empiric variables (binary)}_i, \end{aligned}$$

where  $T_i$  denotes exposure status for individual  $i$ , with  $T_i = 1$  indicating a recorded vaccination of the COMIRNATY 2023-2024 Formula and  $T_i = 0$  indicating no recorded vaccination of the COMIRNATY 2023-2024 Formula.

A greedy digit-based matching algorithm will be used, in which patients exposed to the COMIRNATY 2023-2024 Formula are matched without replacement to comparator patients at a given level of precision defined by the number of digits of the PS (Parsons, 2001), to a maximum of 8 decimal places. When no further matches are available at a given level of precision, the number of digits is sequentially reduced until a maximum allowable caliper of 0.1 is reached, thereby ensuring that the matched cohorts are comparable with respect to the underlying measured risk factors. Matching by propensity score will be conducted within

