#### 9.7.2.4. Subgroup Analysis

If sample size permits, the main analysis will be restricted to the following subgroups:

- Individuals with concomitant administration of a non-COVID-19 vaccine (e.g., seasonal influenza, RSV) on cohort entry date; specific analyses will be performed among individuals receiving seasonal influenza vaccine and those receiving RSV vaccine
- Immunocompromised individuals
- Individuals with specific baseline comorbidities, such as a chronic lung, heart, kidney or liver condition; cancer; Down syndrome or other neurological or neurodevelopmental disorders; and blood disorders
- Individuals with prior SARS-CoV-2 infection
- Individuals with prior COVID-19 vaccination
- Pregnant women
- Individuals aged < 18 years
- Individuals aged  $\geq$  65 years

For the subgroup analysis, the propensity score will be included in the model as a covariate, given that some matched strata may be broken by restricting both the COMIRNATY 2023-2024 Formula cohort and the comparator cohort by the above attributes. As with the primary analysis, unconditional Poisson regression will be used, and the model will account for individuals who are included in both groups.

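### The pharmacy (NDC) vaccine list leaves out RSV, pneumococcal and other classes that the parallel CPT list includes, and no list is assigned to the RSV covariate and subgroup

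*Protocol*

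**What the plan says.** Section 17.2.2.1 lists CPT codes by vaccine class. It includes a row for "Respiratory syncytial virus vaccine", one for "Pneumococcal vaccine", meningococcal codes, a tetanus row reading "90696-90703, 90714-90715, 90723", and two zoster codes (90736 and 90750).

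Section 17.2.2.2 is the pharmacy counterpart. It opens with "The below list includes generic vaccine names classified by therapeutic use", says that all NDCs linked to the named generics will be used, and promises to add further vaccines once available.

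The abstract, under Variables, identifies COMIRNATY exposure by "National Drug Codes (NDC) on pharmacy claims or Healthcare Common Procedure Coding System (HCPCS) codes on medical claims". Section 9.4.1, on the pre-adjudicated database, says that pharmacy claims are typically "submitted electronically by the pharmacy at the time prescriptions are filled or vaccinations are administered". The pharmacy claim fields it then lists include NDC and no procedure code.

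These vaccine records are used in three places:
- Section 9.3.1.2 accepts a comparator on a code for another vaccine or an outpatient encounter, and refers to Appendix II for the codes. Section 9.7.2.3 then divides comparators by type of encounter.
- Section 9.7.2.1 includes the propensity score term that begins "RSV vaccination (binary".
- Section 9.7.2.4 promises that "specific analyses will be performed among individuals receiving seasonal influenza vaccine and those receiving RSV vaccine".

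Section 9.3.3 sends the reader to Appendix IV for covariate codes. Appendix IV holds comorbidities and medication history, and no influenza or RSV vaccine list.

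**The concern.** The two lists should describe the same vaccines as seen in two kinds of claim. They do not. Influenza appears in both; RSV appears only among the CPT codes. A variable built from these lists would capture influenza doses from clinics and pharmacies alike, but RSV doses only where a medical claim was submitted.

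Two things are at stake. First, section 9.9 says that influenza and RSV are the only other vaccinations pre-specified in the propensity score model. An RSV term blind to pharmacy doses controls less confounding than that section implies. Second, the RSV subgroup belongs to the concomitant-vaccine part of the Phase 2 secondary objective. It would lose people given both vaccines at one pharmacy visit when the RSV dose is billed by NDC. Pharmacy visits for the omitted classes alone would also fail to bring comparators into the cohort.

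**Working it through.** No sample size, power or alpha figure is involved, and the plan gives no figure to reproduce. The check is a comparison of the two lists, followed by an illustration under assumed shares.

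**Step 1. Lists side by side** (the NDC list has 40 entries)

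| Class | CPT, 17.2.2.1 | NDC, 17.2.2.2 |
|---|---|---|
| RSV | 90380-90381, 90678-90679, 96380-96381 | none |
| Pneumococcal | 90669-90671, 90732 | none |
| Meningococcal | 90619-90621, 90644, 90733-90734 | only combined with hepatitis B and Hib |
| Tetanus-containing | ranges including 90714-90715 | only combined with diphtheria, pertussis and Hib |
| Zoster | 90736, 90750 | live vaccine only |
| Influenza | several ranges | five entries, two of them H1N1 |

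Stand-alone Hib, tick-borne encephalitis, Lyme and Ebola vaccines are also in the CPT list only.

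**Step 2. Could the gap come from text extraction?** The NDC list is essentially alphabetical, and the neighbours are intact where most missing entries would stand: plague then poliomyelitis (pneumococcal), rabies then rotavirus (RSV), measles then mumps (meningococcal), staphylococcus then typhoid (tetanus). Only a recombinant zoster entry would fall at the very end, where a lost line cannot be ruled out from the ordering alone.

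**Step 3. Does the promise to add vaccines cover it?** No. The omitted classes already have CPT codes in the same annex. Version 3.0 is dated 18 March 2026, almost two years after accrual ended on 31 March 2024.

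**Step 4. Effect on each use**
- *Comparator entry.* A pharmacy visit for only an omitted vaccine produces no Appendix II vaccine code, so that visit does not qualify. The person may still enter on another qualifying encounter.
- *RSV propensity score term and RSV subgroup.* No list is assigned to them. Under the only RSV list in the document, doses billed solely by NDC are missed.
- *Influenza.* Captured from both sources. A same-day pharmacy influenza dose keeps a person in the non-COVID-19 vaccine comparator type and in the overall concomitant-vaccine subgroup.

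**Step 5. Illustration.** Let q be the share of RSV doses billed only by NDC and p the true RSV uptake. Both are assumed. Suppose also that every other dose is recorded and none is recorded falsely.
- Capture = 1 - q
- Recorded uptake = p(1 - q)
- Truly vaccinated among those coded unvaccinated = pq / [1 - p(1 - q)]

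With p = 15%:

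| q | Capture | Recorded uptake | Vaccinated among those coded unvaccinated |
|---|---|---|---|
| 30% | 70% | 10.5% | 0.045/0.895 = 5.0% |
| 60% | 40% | 6.0% | 0.090/0.940 = 9.6% |
| 90% | 10% | 1.5% | 0.135/0.985 = 13.7% |

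Over p from 5% to 30% and the same q, the last column runs from 0.015/0.965 = 1.6% to 0.270/0.970 = 27.8%.

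**The case against.** The strongest reply is that section 17.2.2.2 sits under comparator codes, and nothing says that the RSV covariate or subgroup is built from it. Section 9.3.3 also says that other baseline vaccinations in the empiric review are captured through both NDC and CPT codes, so the programs may already look up RSV NDCs. This stands as a limit: the effect on the RSV term and subgroup is conditional. It does not remove the need to act. Section 7 calls this document a combined protocol and SAP, Annex 1 lists no standalone documents, and the covariate appendix has no vaccine list, so no other source is identified.

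The mechanism in section 9.4.1 is described for the interim database, whereas the cohort study uses the ORD. That is fair. The abstract's exposure definition is the better support, and it is stated for COMIRNATY; carrying it over to other vaccines is an inference.

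Pneumococcal, zoster, meningococcal and Td/Tdap vaccines are neither pre-specified covariates nor named subgroups. Section 9.9 discloses that they lie outside the propensity score and offers a review of common codes. That is correct for baseline confounding. The review covers the 25 most frequent codes and feeds only the propensity score; section 9.9 aims it at vaccines other than influenza and RSV. It cannot repair comparator entry or the RSV subgroup.

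Three stronger readings are tempting, and the documents do not support them:
- *Hidden RSV co-exposure contaminates a comparison of COMIRNATY given alone.* No such comparison is planned. Section 9.7.2.4 defines only a subgroup with a concomitant vaccine, and section 9.7.2.3 divides only the comparators.
- *Omitted doses are generally read as no vaccine in the comparator types.* The no-vaccine type needs an outpatient encounter at cohort entry, so this happens only when such a code falls on the same day. Otherwise the visit simply does not count.
- *The vaccinated comparator group as a whole is selected by site of care.* Pharmacy influenza, hepatitis, HPV, MMR, varicella and other vaccines are captured; only the omitted classes are affected.

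**Conclusion.** The mismatch between the two lists is plain on the page and should be corrected. Its direct consequence, if other pharmacy vaccines are found by NDC as COMIRNATY is, is that pharmacy visits for only an omitted vaccine do not qualify comparators. Its consequence for the RSV propensity score term and RSV subgroup is likely but conditional on the Appendix II list being used for them.

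The size cannot be fixed from the document, because the pharmacy share of doses is not given. The figures under the working restate that assumed share as misclassification; they show no effect on any rate ratio. RSV is also one of 26 pre-specified propensity score terms.

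The primary cohort analysis pools all comparator types, so misassignment between types does not change its comparator definition. The SCRI and the COMIRNATY exposure definition do not depend on this list. This is a code-list inconsistency to settle before the final report, planned for 30 April 2026; it does not undermine the study design.

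**What to change.** - In 17.2.2.2, add generic entries, with all associated NDCs, for every vaccine class in 17.2.2.1. RSV is the priority; pneumococcal, recombinant zoster, Td/Tdap/DTaP and meningococcal should follow.
- State in 9.3.3, 9.7.2.3 and 9.7.2.4 that the influenza and RSV covariates, the concomitant-vaccine subgroups and comparator type are defined by a CPT code or an NDC, whichever is present. Either add the influenza and RSV lists to Appendix IV or point from there to Appendix II.
- Check the executed programs. If they already use the fuller set of NDCs, correcting the annex is enough. If they used the shorter list, rerun cohort creation, the propensity score and matching, and the analyses that depend on them.

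The cost is a code-list update and possibly a rerun. No new data are needed.
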